2.0 INTRODUCTION

The nature of acute myeloid leukemia (AML) changes with age. Different cut-offs have been used to define older AML patients, the most common has been age ≥ 60 years. When compared with younger adults, AML in patients aged ≥ 60 years is more frequently preceded by a myelodysplastic syndrome (MDS), has unfavorable cytogenetics, more commonly expresses multidrug resistance, and hence responds less well to chemotherapy [1-3]. In addition, older AML patients are frailer with poor performance status[3] and probably higher comorbidity burden similar to other aging populations [4-6]. As a result, treating aging individuals with AML has been a challenge with only $\leq 10\%$ patient surviving longer than 5 years.

The advent of nonmyeloablative or reduced-intensity conditioning regimens in the past decade has broadened the eligibility criteria for allogeneic HCT to include older and medically infirm patients. Preliminary data on nonmyeloablative allogeneic HCT among small numbers of older AML patients shows 35-50% survival rates at 3-years, better than expected with conventional chemotherapy [7]. However, extrapolation of these results to the general older AML population is difficult, as they include only those patients who were enrolled onto the HCT protocols. Likewise, patients with a relatively high burden of comorbidities are likely excluded from allogeneic HCT, with this selection bias confounding interpretation of HCT results. The percentages of patients not referred for HCT because of lack of insurance coverage, rapidly progressing disease, poor general condition, or physician preference are unknown.

Our primary goal here is to investigate how often older and medically infirm patients, who are diagnosed with AML or high-risk myelodysplastic syndromes (MDS) and treated with induction therapy, undergo allogeneic HCT in four collaborating institutions. We will investigate different factors that might affect the rate of referral to allogeneic HCT. These rates and reasons will be compared to those in younger and healthier AML/MDS patients. Understanding selection bias, we will follow the prospectively enrolled patients for additional 24 months and describe their outcomes comparing allogeneic HCT versus conventional therapy.

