5.3 Tertiary objectives

- 5.3.1 Preliminary therapy data will be used to develop standardized criteria for the definitions of “intensive” and “less-intensive” treatments. Physicians from around the world will be surveyed about their opinion of the intensity of regimens.

Protocol 2368.00

- 5.3.2 Project results will be disseminated per funding agency's request using novel methods. Methods will include social media, websites, videos, and newsletters. Patients may be asked to appear on video. All methods have the possibility of being published or mentioned in publications.
- 5.3.3 Among a subset of patients admitted to the ICU at any time point after induction chemotherapy, evaluation of risk factors associated with 90-day and overall survival after ICU admission. Rates of palliative care referrals in patients with and without ICU admissions will be examined.
- 5.3.4 Comparison of outcomes between patients with secondary AML and patients without secondary AML.

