The NIH Toolbox 4-Meter Walk Gait Speed Test will be used to measure locomotion. Gait speed is an indicator of the health of physiological systems. Patients will be asked to walk four meters at their usual pace for one practice session and two timed trials. This test takes three minutes to administer. Study coordinators will meet the patients at regularly scheduled medical appointments and will ask them to complete this quick assessment. For patients with no scheduled appointments within the range of administering the 4-meter walk test, study coordinators will mail a self-administered walk test sheet to be completed by the patient. Previous studies have shown that a self-administered, adapted walk test (the Home-Heart-Walk) had a strong intra-class correlation coefficient (0.98) with a standard walk test.[80,81] The test was well received by participants who had a median age of 64 (range: 49 – 80) years old.[81] The study concluded that self-administered walk test is a reliable and useful method of collecting physical activity data in a medically-challenged, older population.[81] We will implement the same restrictions used in that study by excluding patients with documented heart failure, unstable angina pectoris, fever, complex arrhythmia, resting diastolic blood pressure of 100 mm Hg or more or unstable gait from performing the test on their own.[81]

This test will be given at:

- 1) Study enrollment.
- 2) All other time points for collection of patient-reported measures; either performed by study staff at a regularly scheduled medical appointment at study institution or self-administered by patients that do not have a coincidentally scheduled medical appointment.

8.1.13 **Outcomes Data:**

8.1.13.1 Alive or deceased.

8.1.13.2 If deceased: cause(s) of death: Root (underlying cause of death), proximate (immediate cause of death), and contributing causes of death.

Protocol 2368.00

- 8.1.13.3 Disease status: remission, relapse, progression, persistent disease supported with by evidence as in (AML response evaluation).
- 8.1.13.4 For recipients of allogeneic HCT:
 - 8.1.13.4.1 Did acute GVHD develop or not?
 - 8.1.13.4.1.1 If yes: date, grade, organs involved, and treatments given for acute GVHD.
 - 8.1.13.4.2 Current status of acute GVHD: active, resolving, resolved.
 - 8.1.13.4.3 Did chronic GVHD develop or not?
 - 8.1.13.4.3.1 If yes: date, grade, organs involved, and treatments given for chronic GVHD.

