 - 8.1.13.5 Current status of chronic GVHD: active, resolving, resolved.
 - 8.1.13.6 Admission to the acute care service within the first 60 days after induction and the first 60 days after consolidation.
 - 8.1.13.7 Admission to the ICU at any time after induction
 - 8.1.13.7.1.1 If yes: dates of admission and discharge from the ICU and hospital, ICU admission diagnosis, most recent AML treatment, and markers of organ failure within 24 hours of ICU admission, including blood counts, blood chemistries, vital signs, and use of life support devices (invasive mechanical ventilation, noninvasive positive pressure ventilation, vasopressors, inotropes, and dialysis). Additionally any positive cultures from 1 week prior to 1 week after ICU admission will be collected.
 - 8.1.13.8 Presence of palliative care referral at any time point after referral to the SCCA.

8.1.14 **Patient-reported QOL measures** (see study document 'Patient Questionnaire Packet):

QOL and symptoms will be assessed longitudinally using 8 measures. All QOL questionnaires will be scored according to the recommendations of the developers. We estimate it will take 15 minutes to complete the questionnaires. Please, see study document 'Patient Questionnaire Packet' for the measures of patient-reported QOL.

The Functional Assessment of Cancer Therapy Bone Marrow Transplant (FACT-BMT, version 4) Scale is a 49-item patient-reported outcome questionnaire that measures QOL in bone marrow transplant patients. The questionnaire includes the standard form of the FACT instrument, namely the FACT-G and a separate BMT scale consisting of 12 items. The BMT scale was enlarged during the validation procedure from 12 to 22 items by McQuellon et al. [82] The FACT-BMT measures physical, functional, social/family and emotional well-being and BMT-specific concerns. All items are rated on a five-point Likert scale. The FACT instrument was recommended by Andrykowski for the investigation of QOL in BMT patients. [83] Patients will be asked to comment on the statements with regard to the time period of the week immediately preceding the specific study time point. To lessen the burden on patients, we will only use the parameters under the standard form of FACT.

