REDCap is located on two servers that are protected by a firewall. Each individual that needs to access REDCap (that is, the study coordinators and investigators) has his/her own account. REDCap implements authentication to validate the identity of end-users that log in to the system. Each account can only have access to projects in REDCap that the person has been invited to. The FHCRC Study Coordinator will determine which part of the project other users have access to. REDCap utilizes an auto-logout setting, which is customizable (default auto-logout time is 30 minutes), and will automatically log a user out of the system if he/she has not had any activity (e.g. clicking, typing, moving the mouse) on his/her current web page for the set amount of time. This prevents someone else from accessing the account and project data if a workstation is left without properly logging out or closing the browser window. To help protect and secure the data stored in REDCap's back-end database, the software application employs various methods to protect against malicious users who may attempt to identify and exploit.

Study Participant Committee:

A number of 12 study participants will be invited to join the study stakeholders. Two participant-stakeholders will be selected randomly from each site and will be involved in research discussions. We will use a random number generator (found at www.randomnumbergenerator.com) to select two numbers between 1 and 100 which will coincide with participants' unique study-related ID. We will generate new numbers for each site. These two participants will be contacted via telephone and will be provided with an explanation about the study objectives and role of stakeholders. If the participant declines participation as a stakeholder, we will use the website to select a new number until we have two participant-stakeholders from each site. Our goal is to

Protocol 2368.00

represent all five sites, both genders, various age intervals above 60 years old, and variable burdens of comorbidities.

The construction of this committee preferably to be completed within the first year of the study enrollment.

The study participant committee members will be asked to evaluate our methods in translating key results into language that can be communicated to other participations, in order to improve participation and minimize losses to follow-up, and to future patients, to ensure broad dissemination of results.

Completion of Expert Opinion Surveys:

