11.0 STATISTICAL CONSIDERATIONS

11.1 Introduction and sample size

To improve the strength of the findings as well as reporting of these findings, we will follow the recommendations of STROBE Statement (see study document ‘STROBE Criteria’) which provides guidelines of how to discuss and report study design, analysis, and findings in manuscript writing.

There is no targeted number for enrollment on this study. Instead, we plan to enroll all eligible patients continuously for duration of 36-40 months from study activation. We anticipate enrolling approximately 1000 patients from all sites but we will allow enrollment of more patients if enrollment rates were unexpectedly higher.

Based on a preliminary screen of the SCCA records over years 2008-2009, approximately 180, 125, 120, and 75 eligible patients with AML were seen annually at the 4 collaborating institutions, respectively, for an annual total of 500 patients. We anticipate enrollment rate of approximately ~65% resulting in a total of approximately 1000 patients observed over 3 years. Based on a preliminary screen, we anticipate that 50% (n=500) will be ≥60 years of age. Among the remaining 500 younger patients, we would anticipate (based on historical distribution of comorbidity scores among HCT recipients) that approximately 35% (n = 170) will have significant comorbidities (scores of ≥3). This suggests that the combined cohort of older or medically infirm patients eligible for studying the rate of receiving allogeneic HCT will be approximately 670 patients over 3 years. **Table 2** shows an estimate of the minimal increment in incidence of HCT detectable with 80% power at the 2-sided 0.05 level of significance, for varying assumptions about the prevalence of the risk factor. These estimates assume a time-to-event analysis, 25% overall incidence at 2 years post-initial therapy and 25% incidence of death without HCT as a competing risk.

Prevalence of risk factor or group	Increment in HCT incidence (HR)
10%	0.17 (1.9)
20%	0.13 (1.7)
30%	0.11 (1.6)
40%	0.10 (1.6)

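### Palliative-care referral (8.1.13.8) is listed without a date and with an SCCA-only start point, so the ICU versus no-ICU comparison in tertiary objective 5.3.3 is open to distortion from event order and survival time

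*Combined protocol and SAP*

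**What the plan says.** Section 5.3.3 (Tertiary objectives) states: "Rates of palliative care referrals in patients with and without ICU admissions will be examined". The protocol gives no hypothesis, test or target for this.

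Section 8.1.13 (Outcomes Data) supplies the variables:

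- 8.1.13.8, referral: "Presence of palliative care referral at any time point after referral to the SCCA".
- 8.1.13.7, ICU: "Admission to the ICU at any time after induction", followed by "If yes: dates of admission and discharge from the ICU and hospital, ICU admission diagnosis, most recent AML treatment".
- 8.1.13.4, acute GVHD: "If yes: date, grade, organs involved, and treatments given for acute GVHD". Chronic GVHD is handled the same way.

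Section 11.3(4) describes models for mortality after ICU admission and a secondary-AML comparison. It gives no method for the referral comparison.

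The study enrolls at the SCCA and at collaborating institutions. Section 11.1 gives annual counts: "approximately 180, 125, 120, and 75 eligible patients with AML were seen annually at the 4 collaborating institutions". It does not say which count is the SCCA's. Where an assessment belongs to one site, the protocol labels it, as the heading of 8.1.3 does for FHCRC patients. Neither 5.3.3 nor 8.1.13.8 carries such a label.

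**The concern.** ICU admission is not a baseline characteristic. A patient must live long enough to be admitted, and a patient who lives longer has more time both to be admitted and to be referred. Two forces then act on an ever/never comparison, whatever the true relation:

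- Surviving to an ICU stay selects patients with more time at risk, which pushes the ICU group's referral proportion up.
- High mortality after the ICU cuts short the time left for referral, which pushes it down.

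A referral made months before the ICU stay also counts the same as one made because of it. Without a date, the analyst can neither separate these cases nor correct for them.

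The start points differ as well. ICU counts from induction and referral counts from arrival at one named centre. A patient treated only elsewhere has no such arrival, so staff at those sites must invent an origin or leave the item blank. At stake is the interpretation of one tertiary comparison.

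**Working it through.** **No plan figure to reproduce.** The documents give no rate, sample size or test for this comparison. The check is a reading of the text plus an illustration under assumed rates.

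**Side by side**

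| | Referral (8.1.13.8) | ICU admission (8.1.13.7) |
|---|---|---|
| Form | present or absent | present or absent, with details |
| Date listed | none | admission and discharge |
| Counted from | referral to the SCCA | induction |
| Start point at other sites | none given | the same, induction |

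**Share of patients outside the SCCA.** The annual total is 180 + 125 + 120 + 75 = 500. If the SCCA is the largest site, the others hold (500 − 180)/500 = 64%. If it is the smallest, they hold (500 − 75)/500 = 85%. This range is conditional, since the counts are not tied to named sites. The number of sites also varies: the introduction has "undergo allogeneic HCT in four collaborating institutions", while the participant committee in 9.0 is to "represent all five sites, both genders, various age intervals above 60 years old".

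**Simulation with no true ICU effect.** Each run had 400,000 patients followed for 24 months. The referral hazard was the same before, after and without an ICU stay, so the true rate ratio is 1. All hazards are assumptions except where stated.

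*Set A.* Death hazard = −ln(S)/24 per month. S = 0.34 is the 2-year OS of the registry patients over 60 cited in 3.3, giving 1.079/24 = 0.045. S = 0.50 is an assumed alternative, giving 0.693/24 = 0.029. ICU hazard was 0.01 to 0.02 per month and referral 0.015 to 0.03 per month. After ICU admission the death hazard was unchanged, or multiplied by 8 or 20 for one month, or by 10 for three months.

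| S, ICU, referral hazard | Death hazard after ICU | Referred, ICU | Referred, no ICU | Ratio | Rate ratio with dates |
|---|---|---|---|---|---|
| 0.34, 0.02, 0.015 | unchanged | 24.9% | 17.2% | 1.45 | 1.01 |
| 0.34, 0.02, 0.03 | unchanged | 43.1% | 30.3% | 1.42 | 1.01 |
| 0.34, 0.02, 0.03 | ×8, 1 month | 37.5% | 30.3% | 1.24 | 1.01 |
| 0.34, 0.01, 0.03 | ×20, 1 month | 32.1% | 31.9% | 1.01 | 0.99 |
| 0.34, 0.01, 0.03 | ×10, 3 months | 30.6% | 32.0% | 0.96 | 1.00 |

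Over all 32 scenarios the ever/never ratio ran from 0.96 to 1.45. Between 49% and 75% of referrals in ICU patients came before the ICU stay. With dated referrals and ICU treated as time-dependent (events over person-time in each state), the rate ratio was 0.98 to 1.04.

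*Set B.* ICU hazard was 0.02 per month, referral 0.02 to 0.08, and death 0.04 without ICU and 0.05 to 0.40 after ICU, sustained for the rest of follow-up. The ever/never ratio ran from 0.86 to 1.36; a repeat with fresh random numbers gave 0.87 to 1.34. At a post-ICU death hazard of 0.20 per month it was 1.00 to 1.05. Of the referred ICU patients, 52% to 84% had been referred before the ICU stay. With dates, the rate ratio was 0.98 to 1.02.

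Taken together, the spurious ratio spans about 0.86 to 1.45. It falls on either side of 1 and is close to 1 where the two forces offset each other.

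**The case against.** **A date may be collected anyway.** Section 8.1.13 also lists death and relapse without the word date, yet OS and DFS are primary time-to-event outcomes, so those dates must be recorded. The case report form is not in the documents. This stands: a reader might infer that no referral date will exist, and the text does not prove that. What can be said is that none is listed, although the ICU and GVHD items in the same section do list theirs, and 9.0 says the form should reflect the evaluations described.

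**Outcomes data are collected repeatedly.** Table 1 schedules them at 1, 3, 6, 9, 12, 18 and 24 months. If the flag is refreshed each time, referral can be placed within an interval of 1 to 6 months. This helps in part, but the text does not say the item is refreshed, and two events within one interval would still have no order.

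**The objective is descriptive.** The plan does not ask whether ICU admission changes referral, and the share ever referred in each group is a legitimate quantity. That is fair. It is still a quantity that mixes survival time and event order, and readers will be inclined to compare the two groups.

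**The bias is assumed, not shown.** Also fair. A reader might conclude that the comparison is distorted, or distorted in a known direction. The documents do not support that: they give no ICU, referral or post-ICU death rates. The 0.86 end needs high post-ICU mortality sustained through follow-up; with time-limited excess mortality the ratio did not fall below 0.96.

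**SCCA patients only may have been intended.** Possible, but not stated. Then the scope needs stating, and the absence of a listed date still matters.

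**Conclusion.** The point holds as a gap in the data specification. As written, 8.1.13.8 lists an undated flag with a start point that patients treated only at other sites do not have, and 11.3(4) gives no method that would make up for it. The comparison in 5.3.3 is therefore open to distortion of unknown size and direction. The range of about 0.86 to 1.45 illustrates what could happen under constant, assumed hazards and no true effect; it does not estimate what this study will see.

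The consequence is limited to a descriptive tertiary item, and no primary or secondary result depends on it. The plan already accepts the underlying reasoning: 11.3(2) treats HCT as a time-dependent covariate and adds landmark analyses so that patients are compared after similar survival. Neither approach can be applied properly to ICU status and referral unless referral is dated.

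**What to change.** 1. In 8.1.13.8, replace the flag with the date of first palliative care referral (or none), at any participating site. If the form already holds this date, say so in the protocol.
2. Count referral and ICU admission from one common origin. Start of induction is one option, since 8.1.13.7 already uses it; referrals before that point would be flagged as prior. Moving referral alone to enrollment would leave the two origins different. Define the equivalent date for patients who enter with refractory or relapsed disease (6.1.2).
3. Add to 11.3(4) that referral will be reported as cumulative incidence with death as a competing event, with ICU admission time-dependent or by landmark, and with referrals before and after the ICU stay shown separately.
4. If only SCCA patients were intended, state that restriction in both 5.3.3 and 8.1.13.8.

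The cost is one date field, taken from the same chart as the present flag, and a sentence or two in the analysis section. The downside is slightly more chart abstraction. If the date is not captured during the study, recovering it later means going back to charts at each site.

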Functional status is a component of GA. It is traditionally assessed by performance status (PS) scales in transplant settings. However, results in geriatric oncology have shown PS scales to underestimate the magnitude of functional impairment in older patients when compared to the more comprehensive assessments provided by use of basic (BADL) and instrumental (IADL) activities of daily living [68,69]. IADL, in particular, was shown to predict OS of older patients with newly diagnosed AML independent from age, PS, or cytogenetics [68,69]. Measurement of gait speed is a simple and objective tool that proves to be very useful for predicting functional

Protocol 2368.00

decline, life-expectancy, and mortality after therapy [70]. It was also shown to be as informative as a physical performance battery [71]. Likewise, assessments of cognition, nutrition, psychosocial status, and social support have all been shown to predict treatment tolerance, survival, and ability to comply with treatment instructions.

The prognostic significance of GA has not been adequately tested in the transplant setting. One preliminary small study of 166 patients has shown that GA could uncover additional impairments in health beyond those captured by PS [72]. However, the study collected data on patients aged from 50 years, and only 4 of these were aged ≥ 70 years. Identifying those components of GA that might add prognostic information to current pre-transplant assessment tools while not adding a substantial burden on patients or transplant teams requires an adequately-sized national study. We will use here the Fried Frailty index to capture frailty among all patients and domains to cover physical, cognitive, psychosocial, and other geriatric problems among patients who are 60 years or older.

3.6 Introducing the use of Comorbidity Indices in Comparative Effectiveness Research of allogeneic HCT:

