- 4) After approximately 6 months from study enrollment and, if necessary, adjusted within a limit of 30 days to have this assessment done prior to treatment with either allogeneic HCT or additional non-transplant therapies.
- 5) At 3, 6, 12, and 18 months after day 0 of allogeneic HCT for recipients of HTC or at 9, 12, 18, and 24 months from study enrollment for patient not treated with HCT.

8.1.17 **Frailty**

Frailty will be evaluated according to the five criteria proposed by Fried,[67] following the original cut-off points, with some modifications[102]: 1) Unintentional weight loss (Shrinking) of $\geq 5\%$ in the last year. 2) Low energy (Exhaustion): Based on two questions asking about interest or pleasure in doing things and asking about feeling down, depressed or hopeless. Those who answered "more than half of the days" or "nearly every day" to at least one of these questions were considered to meet this

Protocol 2368.00

criterion. 3) Weakness: The Timed Up and Go is a performance test of physical mobility. The test measures how many seconds it takes an individual to stand up from a standard armchair (approximate seat height of 46 cm), walk a distance of 3 m (10 ft), turn, walk back to the chair, and sit down again. The test was originally reported by Mattias et al., and subsequently modified by Podsiadlo et al.[103] to be a timed test. In a population of frail, community-dwelling older adults, there was good interrater and intrarater reliability (intraclass correlation coefficient = 0.99 for both). The Timed Up and Go score correlated to the scores on the Berg Balance Scale (correlation coefficient [r] = -0.72), gait speed (r = -0.55), and Barthel Index of ADL (r = -0.51) [103]. Guralnik et al.[71] reported gait speed as an important predictor of disability. Duration <7 seconds will meet criteria of frail for weakness. 4) Slowness: Calculated after walking 4 meters, adjusted for sex and height, according to Fried. The cut-off points for 4 meters were established as, in men: height \leq 173 cm and time 0.65 m/s; height >1.73 cm and time 0.76 m/s; and for women: height \leq 1.59 cm and time 0.65 m/s; and height >1.59 cm and time 0.76 m/s. 5) Low physical activity: will be captured by the MOS Physical Health Scale. Patients scoring in the lowest 20% will be assigned a point for frail for physical activity.

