Based on the above five criteria, which incorporates two performance-based measures (timed up-and-go and walk speed over 4 meters) and three self-report measures (exhaustion, weight loss, and physically frail), range of scores will be 0-5; 1-2 indicates pre-frail, 3-5 indicates frail.

FI score will be assessed at:

- 1) Study enrollment.
- 2) After approximately 6 months from study enrollment and, if necessary, adjusted within a limit of 30 days to have this assessment done prior to treatment with either allogeneic HCT or additional non-transplant therapies.
- 3) At 18 months after day 0 of allogeneic HCT for recipients of HTC or 24 months from study enrollment for patient not treated with HCT.
- 4) If no clinical appointments, the timing can be expanded to within 6 months of the above time points.

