8.1.19 Questions about some geriatric problems only for patients 60 years and older

The questionnaire will ask the following questions:

- 8.1.19.1 Vision
- 8.1.19.2 Hearing
- 8.1.19.3 Other physical problems or illness
- 8.1.19.4 Falls

These variables will be assessed once at:

- 1) Study enrollment

8.1.20 Recovery Survey:

The recovery survey will ask the following questions:

- 8.1.20.1 Marital status
 - 8.1.20.1.1 Change since diagnosis of AML
 - 8.1.20.1.2 Current marital status.
- 8.1.20.2 Work status
 - 8.1.20.2.1 Change since diagnosis of AML
 - 8.1.20.2.2 Current work status.
- 8.1.20.3 Family income
 - 8.1.20.3.1 Change since diagnosis of AML
 - 8.1.20.3.2 Current income.

These variables will be assessed once at:

- 1) 24 months from study enrollment.

Protocol 2368.00

Table 1: Timing of Study Evaluations*

	Timing of assessments							
		Months						
Measures	Enrollment	1	3	6 ∇	9 ∇	12 ∇	18 ∇	24 ∇
	£							
Patient-reported socio-demographic & health behaviors survey	X							
AML diagnostic features	X							
HCT-CI, comorbidities, and laboratory tests	X		X	X				X
KPS	X		X	X	X	X	X	X
Physician preference surveys	X	X	X	X**				
Patient Preference Survey	X	X	X	X**				
Availability of donor, and its type	X	X		X				
Treatment details		X	X	X	X	X	X	X
AML response evaluations		X	X	X	X	X	X	X
Toxicity grading		X	X	X	X			X

Protocol 2368.00

QOL measures in Questionnaire Packet	X	X	X	X	X	X	X	X
Function measures (Walk Test)	X	X	X	X	X	X	X	X
Timed Up-Go test for FI calculation	X			X				X
Cognition in older patients	X					X		X
Geriatric problems in older patients	X							
Outcomes data		X	X	X	X	X	X	X
PFT, Blood Tests, Urine test (FH site only)	X							
Patient-reported Recovery survey								X

*All dates of assessments are recommended dates that could be adjusted (within a limit of 30 days) to take into account suitability of patients' clinical status and reasonable recovery of peripheral blood counts.

[figure not shown]
[figure not shown]
**Assessment will be done if the patient has not undergone HCT

£Assessment should be done after enrollment and preferably before the start of treatment. However, a grace period of one week after the start of treatment is allowed to consent the patient and introduce the assessments. Surveys should be completed by the patients based on their experiences before start of treatment and they should be returned as soon as possible after being completed.

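### The weakness item of the frailty index is scored backwards: a Timed Up and Go under 7 seconds, which is a fast result, earns the frail point

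*Combined protocol and SAP*

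**What the plan says.** Section 8.1.17 (Frailty) builds a five-item score. Item 3, weakness, uses the Timed Up and Go: the seconds a person needs to rise from an armchair, "walk a distance of 3 m (10 ft), turn, walk back to the chair, and sit down again". The paragraph then reports how the test relates to other measures: -0.72 with the Berg Balance Scale, followed by "gait speed (r = -0.55), and Barthel Index of ADL (r = -0.51". It also cites gait speed as a predictor of disability. The scoring rule follows: "Duration <7 seconds will meet criteria of frail for weakness".

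Item 4, slowness, uses the 4-meter walk with cut-offs of 0.65 or 0.76 m/s, depending on sex and height. One of these is printed as "height >1.73 cm and time 0.76 m/s". Section 8.1.12 adds about that walk: "Patients will be asked to walk four meters at their usual pace".

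The five items are summed: "range of scores will be 0-5; 1-2 indicates pre-frail, 3-5 indicates frail". Table 1 lists a row "Timed Up-Go test for FI calculation" at enrollment, 6 and 24 months. By its footnote and Section 8.1.17, the last of these becomes 18 months after day 0 for transplant recipients. On the purpose of the score, Section 3.5 says: "We will use here the Fried Frailty index to capture frailty among all patients".

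**The concern.** A frailty point should go to the worse performance. Here it goes to the better one, although the text just before the rule shows that more seconds goes with slower gait. No other section restates or corrects the rule.

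A scorer or programmer who follows the text literally would add a point for patients who finish quickly and none for patients who finish slowly. The error is systematic. It narrows the difference in score between fit and unfit patients, and it sets the two performance-based items of the index against each other. Any analysis using the frailty score would inherit this, whether frailty is described, used as a predictor of reaching transplant, or used for adjustment.

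**Working it through.** The plan has no sample-size or power figure to reproduce here. The check is on the direction of a scoring rule and its consistency with the neighbouring item.

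**Inputs, all from Section 8.1.17**
- Weakness rule: time < 7 s earns one point.
- Distance walked: 3 m out + 3 m back = 6 m, plus standing, turning and sitting.
- Correlation of the test with gait speed: -0.55.
- Slowness cut-offs: 0.65 and 0.76 m/s.
- Categories: 1-2 pre-frail, 3-5 frail.

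**Step 1: direction.** The measure is elapsed time, and its correlation with gait speed is negative, so a longer time goes with slower gait. Section 8.1.12 treats gait speed as a marker of health. A longer time is therefore the worse result, and the printed rule rewards the wrong end. The balance and daily-living correlations (-0.72 and -0.51) agree if higher scores on those scales mean better function. The documents do not say so, but the gait-speed correlation is enough.

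**Step 2: speed implied by the rule.** Speed = distance / time. With no time allowed for standing, turning and sitting, finishing in under 7 s needs more than 6/7 = 0.857 m/s. If those movements take an assumed 1, 2 or 3 s, the required speed rises to 6/6 = 1.0, 6/5 = 1.2 or 6/4 = 1.5 m/s.

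**Step 3: comparison with slowness.** Time for the 6 m alone at the slowness cut-offs:
- 6 / 0.76 = 7.9 s
- 6 / 0.65 = 9.2 s

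Both exceed 7 s. A patient at or below a slowness cut-off, walking at the same pace in both tests, cannot earn the weakness point as written. The highest total is then 3 (the self-report items) + 1 (one performance item) = 4, not 5. With the inequality reversed, and 7 s kept only for illustration, the same patient would score on both items.

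**Step 4: effect on the category.** Let s be the sum of the other four items. The weakness point moves the total between s and s + 1. The category changes only when:
- s = 0: total 0 or 1, so no points or pre-frail. One pattern of the four items.
- s = 2: total 2 or 3, so pre-frail or frail. Patterns: 4!/(2! × 2!) = 6.

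That is 1 + 6 = 7 of 2^4 = 16 patterns. This counts item patterns, not patients.

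**Step 5: who is mis-scored.** Suppose the intended rule is that times above some cut-off of 7 s or longer earn the point. Patients under 7 s then gain a point wrongly, patients above the intended cut-off miss one, and anyone between 7 s and that cut-off is scored correctly.

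**The case against.** The strongest reply is that this is one wrong symbol. The item is headed as weakness, the next as slowness, and the paragraph plainly regards slow walking as worse, so nobody chose to score fast patients as frail. The programmed scoring may already be right. Section 11 never names frailty. Its only route into a planned analysis is the general reference in Section 11.2 to candidate predictors, and the 4-meter gait speed is recorded separately and is unaffected. All of this is fair. It limits the consequence but leaves the printed rule wrong, and that rule is the operative scoring definition.

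A second reply concerns the unreachable maximum. The plan sets the usual pace for the 4-meter walk but states no pace for the Timed Up and Go. The walk may be self-administered at home, and frailty timing may stretch to within 6 months when there is no appointment. A correlation of -0.55 means only about 0.55² = 30% shared variance. This stands: the maximum of 4 holds only at equal pace. The direction argument does not need it.

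Third, the less-than sign could be a PDF reading error. That cannot be fully excluded, but other inequality signs in the paragraph came through, and checking the programmed scoring would settle it. The same caution applies more strongly to the missing direction of the speed cut-offs, because some symbols were lost in Section 8.1.18.

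**Conclusion.** The concern holds: as written, the weakness item is reversed. The conclusion rests on the definition of the test in seconds and on the sign of its correlation with gait speed, both in the same paragraph as the rule.

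The size is bounded. Each total is wrong by at most one point, and the category changes only when the other four items sum to 0 or 2. The number of patients misclassified cannot be computed, because the documents give neither the intended cut-off nor the distribution of times. Sample size, power and significance level are not touched, and no effect on a primary result is shown. The harm is confined to analyses that use the frailty score, and it assumes that scoring followed the printed text.

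Two smaller slips sit in the slowness item. Heights are printed as 1.73 cm and 1.59 cm beside 173 cm, and the speed cut-offs are labelled as times with no stated direction.

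**What to change.** Amend Section 8.1.17 so that a longer Timed Up and Go time meets the weakness criterion. Confirm the cut-off against the instrument's source, since the documents do not establish whether 7 s is the intended value. Compare the result with the scoring actually programmed. If the program follows the printed rule, re-score from the recorded seconds at enrollment, 6 months and the final assessment (24 months, or 18 months after day 0 for transplant recipients).

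In the same edit, print the heights as 173 cm and 159 cm, label the slowness cut-offs as speeds, and state that speeds at or below them count as slow, if the source confirms this.

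The cost is a short protocol correction, a check of the scoring code and, if needed, a re-score. No new assessments are required, provided the raw seconds were stored and not only a yes/no result; the documents do not say which.
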